#### 7.2.1. Benzyl Alcohol Dose

The amount of benzyl alcohol in the formulation was compared with the amount delivered by Increlex ([Increlex Product SmPC](#)), an approved product containing phenol and benzyl alcohol. Each mL of Increlex contains 10 mg/mL mecasermin and 9 mg/mL benzyl alcohol.

Based on Posology, the recommended starting dose of mecasermin is 0.04 mg/kg of body weight twice daily by an SC injection. If no significant adverse reactions occur for at least one week, the dose may be raised in increments of 0.04 mg/kg to the maximum dose of 0.12 mg/kg given twice daily. Doses greater than 0.12 mg/kg BID should not be exceeded. [REDACTED]

[REDACTED] is well within these already approved dose ranges given to small children for Increlex.

#### 7.2.2. Setmelanotide Dose

The dose level of setmelanotide used in this trial will be based on the weight bands for the 2- to <6- year-old patients ([Table 3](#)) to ensure the exposure is similar to that observed for adults dosed at 2 to 3 mg setmelanotide QD. [REDACTED]

[figure not shown]
**Table 3: Dosing Schedule for Patients 2- to <6 Years Old**

[figure not shown]
	Maximum Dose
	0.5 mg/day
	1.0 mg/day*
	1.5 mg/day
	2.0 mg/day

[figure not shown]
\* [Redacted]

[Redacted]

[figure not shown]

[figure not shown]

[figure not shown]

[figure not shown]

Refer to the IB for additional information on the toxicology of setmelanotide in mPEG-DSPE.

### 7.3. Treatment Administration

Setmelanotide will be administered as a SC injection. All patients will begin treatment at a dose of 0.5 mg of setmelanotide per day. Patients will then increase their dose by 0.5 mg increments, every 2 weeks, as described in the SoA (Table 1). The maximum dose level of setmelanotide used in this trial will be based on the weight bands for the 2- to <6-year-old patients to support an exposure similar to that observed for adults dosed at 2 to 3 mg setmelanotide QD. The maximum dose level in this trial for patients who weigh [REDACTED] will be 0.5 mg, 1.0 mg, 1.5 mg and 2.0 mg QD, respectively.

If a patient's weight decreases to below 15 kg during the trial, the Investigator and Sponsor will discuss the patient's status and will jointly determine if a patient should continue the current dose, decrease the dose or discontinue treatment with setmelanotide temporarily or permanently. A dose reduction to 0.25 mg can be considered in such scenarios or in case of safety or tolerability concerns. These dose adjustments are considered adequate to help attain and maintain appropriate body weight in growing pediatric patients.

At the discretion of the Investigator, a patient may temporarily pause the dose escalation at any step prior to reaching their final maintenance dose, for safety or tolerability reasons, or due to achieving adequate weight loss. The dose may continue to be evaluated and adjusted, at the

discretion of the Investigator, as [REDACTED] and 2.0 mg QD, according to their respective weight.

During the Dose Escalation visits (Weeks 2, 4 and 6 in SoA), the dose is to be increased as appropriate for the individual patient's weight at enrollment. At each visit, the decision to escalate the dose is to be based on patients' tolerability and health status. If a patient has already achieved their final maintenance dose prior to Week 4 or 6, the subsequent visits will not be considered "dose escalation" visits, but rather standard visits.

It is recommended to maintain a 2-week interval between the dose escalations, although the dose may be escalated at a longer interval (i.e., within 4 weeks), depending on patient weight and tolerability.

If it is not possible to achieve the final maintenance dose by Week 6 due to tolerability concerns (e.g., severe gastrointestinal adverse events) or due to potential effects on weight or hunger levels, the dose may be escalated over the next visit(s) (Week 8, etc.), with trial visits continued as per protocol. There is no need to perform an Unscheduled Visit 2 weeks after escalation of the dose unless it is required for patient safety.

#### **7.4. Concomitant Medications**

Any medication or vaccine (including over-the-counter or prescription medicines, vitamins, and/or herbal supplements) that the patient is receiving at the time of enrollment or receives during the trial must be recorded along with:

- Reason for use
- Dates of administration including start and end dates
- Dosage information including dose and frequency

The Medical Monitor should be contacted if there are any questions regarding concomitant or prior therapy.

The dose of concomitant medications used during the trial should not be changed and new concomitant medications should not be started during the trial, unless necessary to treat an AE.

Patients should not make significant changes to their diet or exercise routines during the trial.

#### **7.5. Treatment Compliance**

Treatment compliance will be recorded by the pediatric patient's caregiver. A daily question querying whether the patient completed their daily injection will be asked via electronic diary. With Sponsor approval, paper versions can be used, if required.

#### **7.6. Randomization and Blinding**

This is an open-label trial with a single treatment arm, therefore there is no randomization and the treatment is unblinded.

## **8. ASSESSMENTS**

Trial procedures and their timing are summarized in the SoA ([Table 1](#)). Adherence to the trial design requirements, including those specified in the SoA, is essential and required for trial conduct.

All screening evaluations must be completed and reviewed to confirm that potential patients meet all eligibility criteria. The Investigator will maintain a screening log to record details of all patients screened and to confirm eligibility or record reasons for screening failure, as applicable.

When scheduled at the same time point, the order of procedures should be as follows: obtain vital signs, perform 12-lead ECG, and then perform blood draws (at the specified time point, if applicable). Adjustments may be made depending upon specific circumstances and in consultation with the Sponsor.

A visiting home nurse may assist with injections at home if requested by families, provided that a caregiver needs or desires assistance, and this is acceptable to the investigative site.

Immediate safety concerns should be discussed with the Sponsor immediately upon occurrence or awareness to determine if the patient should continue or discontinue trial treatment.

### **8.1. General Trial Assessments**

#### **8.1.1. Informed Consent/Assent**

A complete description of the trial is to be presented to the parent/legal guardian(s) of each potential patient and signed and dated. Informed consent/assent is to be obtained before any study-specific procedures are performed. In the event of an amendment to the informed consent, re-consent by the patient or parent/legal guardian is necessary.

A copy of the informed consent/assent must be provided to the patient or the parent/legal guardian.

#### **8.1.2. Demographic/Medical History**

Medical history and demographic data including the patient's gender, race, date of birth, and concomitant medication use will be obtained for all patients during the Screening Period.

The medical history should be updated on Day 1 prior to first dose of trial drug, to assess continued trial eligibility and adherence to final inclusion/exclusion criteria. This medical history update includes a review for changes from Screening as well as a review of the patient's recent medication use to assess whether any changes have occurred since the previous visit.

Additionally, weight-related history including growth charts since birth should be obtained and reported.

#### **8.1.3. Genetic Sample**

A blood sample will be obtained at baseline to confirm a genetic diagnosis. However, patients may be entered into the trial with documentation of previously obtained genetic results.

#### **8.1.4. Physical Examination**

A complete physical examination will be conducted at Screening and at the EOT visit. At other timepoints, an abbreviated examination will be performed. The abbreviated examination should focus on heart, lungs, skin, neurologic examination, and any areas of previous abnormal findings, noting any changes from baseline. Tanner staging should be performed at Screening and at the EOT visit (Week 52) visit. It may be done at additional visits, at the discretion of the Investigator.

#### **8.1.5. Electrocardiogram (ECG)**

A single 12-lead ECG will be performed at the time points designated in the SoA ([Table 1](#)). If an ECG is not practical in a young patient, it may be replaced by a rhythm strip and HR and pulse rate interval should be documented. The ECG (or HR and pulse rate) results will be interpreted locally by the investigator or qualified designee and documented in the patient's medical records.

#### **8.1.6. Comprehensive Skin Evaluation**

A comprehensive skin evaluation will be performed by the Investigator or qualified designee at Screening. The skin exam should include a full body skin exam (head-to-toe skin examination). Any concerning lesions identified during the Screening Period will be biopsied and results must be known to be benign prior to the first dose of setmelanotide. If the pre-treatment biopsy results are of concern, the patient will be excluded from the trial. Additionally, any new lesion or change in an existing lesion identified during the trial must be evaluated by a dermatologist and biopsied, if clinically indicated in the opinion of the dermatologist.

#### Protection from Sun

Skin hyperpigmentation, or tanning, was observed in the cynomolgus monkey toxicology and human trials. These events were reversible upon cessation of trial drug. However, it is still uncertain if exposure to sunlight might exacerbate the tanning effects of setmelanotide. Therefore, patients are advised to use sunscreen and/or to wear protective clothing to avoid excessive exposure of their skin to sunlight and to avoid sun-tanning.

#### **8.1.7. Fitzpatrick Scale**

Each patient is to be categorized for skin type according to the Fitzpatrick scale ([Fitzpatrick1975](#)) at timepoints listed in the SoA. The Fitzpatrick Scale is presented [Appendix 3](#).

### **8.2. Efficacy Assessments**

#### **8.2.1. Weight and Height**

Weight (kg) and height (cm) will be recorded at the time points designated in the SoA ([Table 1](#)). All measurements will be done in triplicate at each time point.

Weight should be measured after patients have attempted to empty their bladders and after fasting for at least 8 hours. Patients are to wear light clothing or underwear and no shoes, with empty pockets, and will be weighed at approximately the same time of day. All measurements will be recorded to the nearest 10th of a decimal place if reported with a digital scale, or half kg with a mechanical scale.

Whenever possible, the same scale should be used throughout the trial, including the Screening visit, and should be calibrated on a regular basis per manufacturer's specifications.

Patient's weight will be monitored closely during the trial. If a patient's weight decreases to below 15 kg, the Investigator and Sponsor will discuss the patient's status and will jointly determine if that patient should continue the current dose, decrease the dose or discontinue treatment with setmelanotide temporarily or permanently. A dose reduction to 0.25 mg QD can be considered in such scenarios or in case of tolerability concerns. These dose adjustments are considered adequate to help attain and maintain appropriate body weight in growing pediatric patients

Height (cm) will be measured without shoes, socks, or hats, using a wall-mounted stadiometer. The stadiometer should be calibrated by site personnel on a daily basis prior to height assessment. All measurements will be done in triplicate at each time point and recorded to the nearest half centimeter. Both weight and height measurements will be used to determine BMI and BMI-related assessments (i.e., Z-score and percentiles).

### **8.2.3. Trial questionnaires**

[figure not shown]

### **8.2.3.2. Ages & Stages Questionnaires®, Third Edition (ASQ®-3)**

The ASQ-3 is a developmental screening tool that assesses developmental progress in children between one month to 5 ½ years (). The ASQ-3 is intended for use at six-month intervals between 6 months and 3 years of age, and then at one-year intervals through age 5.

For patients who enter the study at ages between 2 years and 3 years, the ASQ-3 will be administered at the Baseline visit, Week 28 visit and EOT Visit. For patients who enter the trial between the ages of 3 and 6 years old, the ASQ-3 will only be administered at the Baseline visit and EOT visit.

Timepoints are as depicted in the SOA (Table 1).

## **8.3. Safety Assessments**

### **8.3.1. Vital Signs**

Vital signs include systolic and diastolic blood pressure (BP), HR, respiration rate and body temperature (°C). Vital signs will be obtained in the sitting position following at least 5 minutes of rest at each time point designated in the SoA (Table 1).

All BP and HR measurements will be taken in triplicate, approximately 2 minutes apart. When possible, BP should be taken in the non-dominant arm throughout the trial, using the same methodology (automated or manual) and ensuring that an appropriately sized cuff is used.

Repeat measures and more frequent monitoring can be implemented for significant increases in BP or HR.

[figure not shown]
### **8.3.2. Laboratory Assessments**

Safety laboratory test parameters to be evaluated are listed in [Table 7](#).

The Investigators will adhere to the site-specific blood volume limits for safety laboratory and [REDACTED] analyses to ensure minimal distress to the pediatric patients. Due to the age of the children, it may not be possible to collect all labs at every trial visit. Screening may be completed over multiple days, to complete the required assessments. After enrollment, if all laboratory tests are not possible, then the tests should be collected in the following order: safety, anti-drug antibodies, [REDACTED]. If it is not possible to collect the safety laboratory tests on two consecutive visits, the patient should be discussed with the Sponsor. To allow for pre- and post-dose sampling, patients will attend the site visit having fasted for an 8-hour time period without injecting the trial product. On the day of the site visit, dosing will be conducted on site.

**Table 7: Safety Laboratory Tests**

Hematology	

 
• Complete Blood Count with Differential:                             
 
– Hematocrit
 
– Hemoglobin
 
– White Blood Cells with differential
 
– Red Blood Cells
 
– Platelet Count
 
 
 
	
Serum Chemistry	

 
• Sodium
 
• Potassium
 
• Chloride
 
• Carbon dioxide
 
• Creatinine
 
• Blood urea nitrogen
 
• Glucose
 
• Calcium
 
• Phosphorus
 
• Thyroid stimulating hormone
 
	
 
• Alkaline phosphatase
 
• Aspartate aminotransferase
 
• Alanine aminotransferase
 
• Gamma glutamyl transferase
 
• Creatine phosphokinase
 
• Total and direct bilirubin
 
• Lactate dehydrogenase
 
• Albumin
 
• Total protein
 
• Uric acid
 

Urinalysis	

 
• Color
 
• Appearance
 
• Specific Gravity
 
• pH
 
• Blood
 
• Ketones
 
	

## **8.5. Anti-Drug Antibodies**

Blood samples for analysis of ADAs will be collected at the time points specified in the SoA. All samples should be collected before trial treatment administration on the day of collection. Any patient with a positive ADA will be followed every 3 months after the ADA sample analysis until resolution of the ADA (ie, no measurable ADA response).

## **8.6. Adverse and Serious Adverse Events**

Adverse events (AEs) will be monitored throughout the trial. AEs will be recorded in the eCRFs from Screening through the EOS visit. AEs that occur after the start of trial drug administration will be considered treatment-emergent adverse events (TEAEs). Serious AEs (SAEs) will be recorded through to the EOS visit. All AEs should be monitored until they are resolved or are clearly determined to be due to a patient's stable or chronic condition or intercurrent illness(es).

All trial sites will be provided with the contact information of key trial personnel to be contacted in case of emergencies.

### **8.6.1. Definition of Adverse Events**

#### **8.6.1.1. Adverse Event (AE)**

An AE is defined as any untoward medical occurrence associated with the use of a drug in humans, whether or not it is considered drug related. Patients/caregivers will be instructed to contact the Investigator at any time after a patient has been enrolled, before treatment, during treatment, or within 30 days following the cessation of treatment, if any symptoms develop.

A TEAE is defined as any event not present before exposure to trial drug or any event already present that worsens in intensity or frequency after exposure.

A suspected adverse reaction is any AE for which there is a reasonable possibility that the trial drug caused the AE. For the purposes of investigational new drug safety reporting, "reasonable possibility" means that there is evidence to suggest a causal relationship between the trial drug and the AE. A suspected adverse reaction implies a lesser degree of certainty about causality than an adverse reaction.

An adverse reaction is any AE caused by a trial drug. Adverse reactions belong to a subset of all suspected adverse reactions and indicate that there are reasons to conclude that the trial drug caused the event.

An AE or suspected adverse reaction is considered "unexpected" if it is not listed in the Reference Safety Information section of the Investigator brochure or if it occurs with specificity or severity that has not been previously observed with the trial drug being tested; or, if an Investigator brochure is not required or available, the AE or suspected adverse reaction is not consistent with the risk information described in the general investigational plan or elsewhere in

the current application. For example, under this definition, hepatic necrosis would be unexpected (by virtue of greater severity) if the IB referred only to elevated hepatic enzymes or hepatitis. Similarly, cerebral thromboembolism and cerebral vasculitis would be unexpected (by virtue of greater specificity) if the IB listed only cerebral vascular accidents. “Unexpected,” as used in this definition, also refers to AEs or suspected adverse reactions that are mentioned in the IB as occurring with a class of drugs or as anticipated from the pharmacological properties of the drug but are not specifically mentioned as occurring with the particular drug under investigation.

All AEs that occur after any patient has been enrolled, before treatment, during treatment, or within 30 days following the cessation of treatment, whether or not they are related to the trial, must be recorded on forms provided by the Sponsor.

#### **8.6.1.2. Serious Adverse Event (SAE)**

An SAE is an AE occurring during any trial phase (i.e., baseline, treatment, washout, or follow-up), and at any dose of the investigational product, comparator or placebo, that fulfills one or more of the following criteria:

- Results in death
- It is immediately life-threatening
- Note: “Life-threatening” refers to a situation in which the subject was at risk of death at the time of the event; it does not refer to an event which might have caused death if it were more severe.
- It requires in-patient hospitalization or prolongation of existing hospitalization
- Note: AEs requiring hospital admissions that are less than 24 hours in duration do not meet this criterion. A scheduled hospitalization for a pre-existing condition that has not worsened during participation in the trial does not meet this criterion. Pre-planned hospitalizations for an elective medical/surgical procedure or routine check-ups do not meet this criterion.
- It results in a persistent or significant incapacity or substantial disruption of the ability to conduct normal life functions
- It is a congenital anomaly/birth defect
- It is an important medical event that may jeopardize the patient or may require medical intervention to prevent one of the outcomes listed above.

Note: Important medical events are those that may not result in death, be life threatening, or require hospitalization but may be considered serious when, based upon appropriate medical judgment, they may jeopardize the subject and may require medical or surgical intervention to prevent one of the outcomes listed in this definition. Examples of such medical events include allergic bronchospasm requiring intensive treatment in an emergency room or at home, blood dyscrasias or convulsions that do not result in inpatient hospitalization, or the development of drug dependency or drug abuse

All SAEs that occur after any patient has been enrolled, before treatment, during treatment, or within 30 days following the cessation of treatment, whether or not they are related to the trial, must be recorded on forms provided by the Sponsor.

### **8.6.2. Relationship to Trial Drug**

A medically-qualified Investigator must assess the relationship of any AE (including SAEs) to the use of the investigational product, as related or not related, based on clinical judgment and using all available information, and may include consideration of the following factors:

- Possible alternative causes of the AE, including the disease under treatment, pre-existing conditions, concomitant use of other drugs, and presence of environmental or genetic factors
- The temporal association between drug exposure and onset of the AE
- Whether the manifestations of the AE are consistent with known actions or toxicity of the investigational product
- Dechallenge: The AE resolved or improved with decreasing the dose or stopping use of the investigational product. Judgment should be used if multiple products are discontinued at the same time
- Rechallenge: The AE recurred or worsened upon re-exposure to the investigational product.

The causal relationship between the trial drug and the AE will be assessed using one of the following categories:

**Not Related:** An AE is not associated with trial drug if:

- Temporal relationship is lacking (e.g., the event did not occur within a reasonable time frame following administration of the trial drug); or
- Other causative factors more likely explain the event (e.g., a pre-existing condition, other concomitant treatments); or
- Dechallenge was either not clinically indicated or did not result in clinical improvement; or
- AE did not reoccur upon rechallenge (if applicable).

**Related:** An AE is attributed to the trial drug if:

- There is a positive temporal relationship (e.g., the event occurred within a reasonable time frame following administration of trial drug); and
- The AE is more likely explained by the investigational product than by another cause (i.e., the AE shows a pattern consistent with previous knowledge of the investigational product or the class of the investigational product), or the event improved on dechallenge and/or re-occurred upon rechallenge (if applicable).

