### **10.3.4 Relationship to Study Drug**

TEAEs will also be summarized by relationship to study drug and will follow the same methods specified in [Section 10.3.2](#). The relationship of the TEAE is classified into two categories of Related and Not Related. If the relationship assessment is missing, the relationship will be considered related. Related TEAEs will also be summarized by MedDRA SOC, PT and maximum severity (defined in [Section 10.3.3](#)). If the patient experiences both a related and not related TEAE within a particular SOC or PT, only the related TEAE will be summarized in the table.

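### One *Not Related* criterion in protocol 8.6.2 turns on how an event was managed, not on its cause, so a single adverse event can meet both causality categories

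*Protocol*

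**What the plan says.** Protocol 8.6.2 sets up a forced choice: "The causal relationship between the trial drug and the AE will be assessed using one of the following categories". It defines two categories.

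- *Not Related* applies if any one of four criteria holds: no temporal relationship; a likelier alternative cause; no recurrence on rechallenge, where applicable; and, third in the protocol's list, "Dechallenge was either not clinically indicated or did not result in clinical improvement; or".
- *Related* needs two things. The first is "There is a positive temporal relationship (e.g., the event occurred within a reasonable time frame following administration of trial drug); and". The second is either "The AE is more likely explained by the investigational product than by another cause" (glossed as a pattern consistent with what is already known of the product or its class), or improvement on dechallenge and/or recurrence on rechallenge.

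The same section says the assessment rests on clinical judgment and all available information. Among the factors to consider it describes dechallenge as covering dose reduction as well as stopping.

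SAP 10.3.4 carries the field forward unchanged: "The relationship of the TEAE is classified into two categories of Related and Not Related". It adds two conservative rules. A missing assessment counts as related. Where a patient has both a related and a not-related TEAE within a SOC or PT, only the related one is summarized. The field feeds the related and serious related summaries in SAP 10.3.1, 10.3.2, 10.3.4 and 10.3.5.

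**The concern.** Two mutually exclusive categories need definitions that cannot both be true of one event. Here they can. The third *Not Related* criterion is met simply because nobody needed to stop or reduce the drug. That is likely to be common for mild events, which protocol 8.6.4 describes as easily tolerated. *Related* does not require that dechallenge was tried, so the same event can satisfy it on timing and pattern.

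What is at stake is the attribution of adverse events in a new age group. The trial is single-arm and open-label (protocol 7.6), so no control rate is available to check the investigators' calls. The pivotal cohort is about 10 to 15 children (protocol synopsis), so moving one child between categories changes a reported percentage by 1/15 = 6.7 to 1/10 = 10 points.

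**Working it through.** The documents give no figure on this point, so the check is one of logic.

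**Inputs, all from protocol 8.6.2**

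- T: positive temporal relationship, yes or no.
- P: drug the likelier explanation, yes or no. Another cause being likelier is taken as the complement.
- D: dechallenge not indicated, improved, or not improved.
- R: rechallenge not done, recurred, or did not recur. It is possible only after a dechallenge.

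**Rules as written**

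- *Not Related* = no T, or no P, or D in {not indicated, not improved}, or R = did not recur.
- *Related* = T and (P, or D = improved, or R = recurred).

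**Feasible profiles.** The D and R pairs number 1 (not indicated) + 3 (improved) + 3 (not improved) = 7. With two levels each of T and P, 7 × 2 × 2 = 28.

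- No temporal link: 14 profiles, all *Not Related* only.
- Temporal link, drug likelier: 7 profiles, all *Related*. Five are also *Not Related*: not indicated (1), not improved (3), and improved without recurrence (1). Two are *Related* only.
- Temporal link, other cause likelier: 7 profiles, all *Not Related*. Four are also *Related*: improved (3), and not improved but recurred (1). Three are *Not Related* only.

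Totals: both 5 + 4 = 9; *Related* only 2; *Not Related* only 14 + 3 = 17; neither 0. The two *Related*-only profiles both require improvement on dechallenge. An event for which dechallenge was never indicated therefore always meets *Not Related*, whatever its timing and pattern.

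**An example from the protocol's own facts.** The section on sun protection records that "Skin hyperpigmentation, or tanning, was observed in the cynomolgus monkey toxicology and human trials". Suppose a child tans on treatment and the drug is continued unchanged because nothing called for a reduction. Timing and known pattern make the event *Related*. The absence of an indicated dechallenge makes it *Not Related*.

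**Do the SAP rules settle it?** The missing-value rule does not apply, because a value has been entered. The within-patient rule compares separate events, so it does not apply to one event that fits both definitions.

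**Effect of possible wording changes on the 28 profiles**

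| Wording | Both | *Related* only | *Not Related* only |
|---|---|---|---|
| As written | 9 | 2 | 17 |
| Not-indicated phrase deleted | 8 | 3 | 17 |
| Dechallenge and rechallenge removed as *Not Related* criteria | 4 | 7 | 17 |
| Same, plus a both-means-*Related* sentence | 0 | 11 | 17 |

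These are counts of logical cases, not frequencies of events.

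**Illustration of size (assumed inputs).** Suppose 80% of N patients have a drug-related TEAE. Suppose a share s of those have only events with no indicated dechallenge, all entered as *Not Related*. The related count becomes 0.8 × N × (1 − s).

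- N = 10: from 8 to 6, 4 or 0.8 for s = 25%, 50% or 90%.
- N = 15: from 12 to 9, 6 or 1.2.

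If no site reads the list literally, s has no effect and the count stays at 8 or 12.

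**The case against.** The best defence is that clinical judgment governs the call and that consistency with the drug's known actions is a listed factor. A sensible investigator may well enter drug-typical tanning as *Related*. This stands in part. It means the text creates an ambiguity with a possible downward effect. A reader might infer that the rule demonstrably biases related counts downward, but the documents do not show that. The judgment clause still sets no precedence, so sites may resolve the conflict differently.

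A second defence is that the events remain visible. This also stands. SAP 10.3.2 tabulates all TEAEs by SOC and PT without a causality filter, SAP 10.7 summarizes hyperpigmentation by visit, and SAP 10.2.3 summarizes injection-site findings. Only the related subset is exposed.

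A reader might also go further and set the likelier-cause wording against protocol 8.6.1.1: "A suspected adverse reaction is any AE for which there is a reasonable possibility that the trial drug caused the AE". The inference would be that any event with a plausible but not leading drug cause has to be entered as *Not Related*. The text does not support that as an absolute, because improvement on dechallenge or recurrence on rechallenge also satisfies the second *Related* condition. Protocol 8.6.1.1 explains reasonable possibility for investigational new drug safety reporting, which is a different purpose. AEs and SAEs are recorded whether or not related (8.6.1.1, 8.6.1.2), and SAEs go to the sponsor within 24 hours (8.6.6). The difference in threshold is at most secondary.

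**Conclusion.** The point holds as an internal contradiction in protocol 8.6.2 that the SAP does not repair. An event with a temporal link and a drug-consistent pattern, for which dechallenge was not indicated, meets both categories. If sites put the *Not Related* list first, the related-TEAE and related serious-TEAE summaries are understated; otherwise they are not.

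The size is unknown. It depends on how sites resolve the conflict and on how many events needed no dechallenge, and the documents give neither. That a typical mild effect would not call for dechallenge is an inference from the severity scale, not a stated fact. The enumeration treats the likelier cause as a two-way choice; it shows where the definitions collide, not how often. The correction is worth making because it is cheap and affects a reported safety summary.

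**What to change.** 1. In protocol 8.6.2, remove the dechallenge and rechallenge items from the *Not Related* criteria and keep them among the factors to consider. Deleting only the not-indicated phrase would leave 8 of the 9 overlapping profiles.
2. Add one sentence that an event meeting both definitions is classed as *Related*. This closes the remaining 4 overlaps and matches the direction of the SAP's rule for missing assessments.
3. By the plan's own dates the trial is near its end: protocol version 5.0 is dated 22 June 2023, and the synopsis estimates last completion in September 2023. Issue the reconciled wording as eCRF guidance, and have investigators re-confirm causality for all adverse events before lock so that all are judged under one rule.
4. Do not limit the re-confirmation to events entered as *Not Related*. A one-way query could itself bias an open-label field. Nor could it be targeted on a recorded alternative cause, since the AE items listed in protocol 8.6.4 and 8.6.5 do not include one.

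The cost is a short wording change and one re-confirmation round. The related-TEAE count may rise. The change concerns classification only and leaves dosing and patient management as they are.
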